6.1.3 Re-induction in either Safety Run-in Phase or Expansion Phase

If a patient in either phase (Phase 1b Safety Run-in, or Phase 2 Expansion) requires re-induction due to not achieving a CR/CRi, they will be treated according to the following schedule. Day numbers below refer to a reset calendar where day 1 refers to the first day of re-induction chemotherapy. The study treatment then continues for a total of 28 days.

| Regimen Description | | | | | |
|-------------------------|--|---|--|----------------------|-------------------|
| Agent | Premedications ; Precautions | Dose | Route | Schedule | Cycle Length |
| Pinometostat | Premedications: ondansetron, dexamethasone | 90 mg/m ² /day, unless 60 mg/m²/day has been previously identified as the maximum tolerated dose after completion of the Safety Run-in Phase | Continuous IV infusion | Days 1-28, weeks 1-4 | 28 days (4 weeks) |
| Daunorubicin (as "5+2") | Premedications: ondansetron, dexamethasone | 60 mg/m ² in 50-100 mL NS | IV over 10-30 minutes | Daily, days 1, 2 | |
| Cytarabine (as "5+2") | Premedications: ondansetron, dexamethasone | 100 mg/m ² /day in 1,000 mL NS (per day) | Continuous IV infusion at rate to achieve 100mg/m ² in 24 hours | Days 1-5 | |

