6.2 Definition of Dose-Limiting Toxicity

DLT Period. DLTs will be evaluated only in the Phase 1b – Safety Run-in Period. The period defined for evaluation of DLT is from the first day of pinometostat administration (day 1) to day 42 after induction, or if a re-induction was attempted, day 42 after re-induction.

Non Hematologic DLT will be determined based on non-hematologic Grade ≥ 3 toxicity related to the study drug alone or the study drug in combination with chemotherapy that occurs within first cycle of the combination. Severity of AEs will be graded according to National Cancer Institute Common Terminology Criteria for Adverse Events (CTCAE) v5. **With the following exceptions:** Grade 3 fatigue < 7 days; correctable electrolyte abnormalities within 72 hours; isolated, asymptomatic AST or ALT (<Grade 4) in the absence of significant bilirubin elevation (<Grade 3) that resolves within 7 days of drug hold; isolated, asymptomatic amylase elevation (<Grade 4) in the absence of lipase elevation (<Grade 3) that resolves within 7 days of drug hold. Pinometostat may be re-initiated in these patients at 60 mg/m² (no matter whether the patient was receiving 90 mg/m² or 60 mg/m²), and re-escalated (if patient was previously on 90 mg/m²; otherwise not applicable) if it does not recur; Grade 3 diarrhea that resolved to \leq Grade 1 or baseline in a week after receiving the maximal supportive therapy based on standard practice Grade 3 nausea and/ or vomiting (excluding need for TPN) that resolved to \leq Grade 1 or baseline in a week after the use of an optimal antiemetic regimen based on standard practice.

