7. DOSING DELAYS/DOSE MODIFICATIONS

No intra-patient adjustment of chemotherapy doses is permitted. No intra-patient escalation of study drug is permitted, except as outlined below and with permission of principal investigator. Dose reduction of pinometostat should occur for grade 3 toxicities possibly related to this agent,

excluding hematologic toxicities and select other toxicities that can occur in the phase 2 expansion portion of the study. These select other toxicities for which a dose adjustment is not required include nausea, vomiting, or diarrhea that is manageable without parenteral or enteral feeding; electrolyte abnormalities that are correctable within 48 hours; and grade 3 infections which are expected in this population.

Daunorubicin and cytarabine are only rarely held during the seven-day intensive induction therapy for AML. Dose modifications to daunorubicin or cytarabine are not recommended for treatment-emergent adverse events, and should be discussed with the principal investigator. For patients with a total bilirubin between 1 and 1.5xULN, the daunorubicin dose may be decreased by 75% after discussion with the principal investigator.

| Event | Management/Next Dose for Pinometostat |
|---------------------|--|
| ≤ Grade 1 | Full dose |
| Grade 2 | Full dose |
| Grade 3 | Hold until recovery of < grade 3, then re-initiate with a one-third dose reduction. For example, if the dose was 90 mg/m ² /day, re-initiate at 60 mg/m ² /day. If the dose was 60 mg/m ² /day, re-initiate at 40 mg/m ² /day. If toxicity reoccurs, therapy should be discontinued. See exceptions in section 6, Dose Limiting Toxicities |
| Grade 4 | Discontinue therapy permanently. |

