9. STATISTICAL CONSIDERATIONS

9.1 Study Design/Endpoints

This study is a multi-site phase 1b/2 study designed to confirm a safe and tolerable dose of pinometostat and to gauge preliminary evidence of efficacy when given as lead-in prior to and contemporaneous with standard intensive induction therapy for newly diagnosed AML with MLL rearrangement. The study design involves a brief safety run-in phase exploring two dosing

schemes, followed by a phase II efficacy expansion. The phase II expansion will use the higher dose-level of the two schedules if tolerated (see definitions below), otherwise, the lower dose-level if tolerated. The phase 1b/safety run-in portion will have a primary endpoint of dose limiting toxicity, while the phase 2 portion will have a primary endpoint of complete remission / complete remission with incomplete count recovery attainment, and will gather additional laboratory correlative data.

The phase 1b safety run-in phase involves dividing patients into two cohorts (cohort 1 and cohort 2) after appropriate screening. The goal will be to identify a maximum tolerated dose for expansion. Dose escalation will occur in the standard cohorts-of-3/3+3 design, which is described below. Cohort 1 will comprise of 3-6 patients and will be treated with pinometostat 90 mg/m² continuous IV infusion (CIVI) on days 1-7, then decrease dose to 60 mg/m² CIVI for days 8-35, along with daunorubicin 60 mg/m² daily on days 8-10 and cytarabine 100 mg/m² CIVI on days 8-14. Cohort 2 will comprise of 3-6 patients and will be treated with pinometostat 90 mg/m² CIVI on days 1-35, along with daunorubicin 60 mg/m² daily on days 8-10 and cytarabine 100 mg/m² CIVI on days 8-14.

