Safety and tolerability evaluation and dose escalation for phase 1b will be performed in the usual 3+3 fashion. See Figure 1. Briefly, 3 patients will be enrolled on cohort 1. If zero of three patients experience dose-limiting toxicities (DLT) on pinometostat, proceed to enroll cohort 2. If one of three patients experience DLT, enroll an additional three patients for a total of six patients on cohort 1. If still only one of six total patients experience DLT, proceed to enroll cohort 2. If 2 or more (of either three total or six total patients) experience DLT, accrual will be stopped and a safety review and consideration of further dose level reductions will be discussed between PI, CTEP, and stakeholders. Cohort 2 will be evaluated likewise, except that no further dose level increases of pinometostat will be made, and if toxicity is unacceptable in cohort 2, the dosing plan of pinometostat for cohort 1 will move forward into the expansion phase. Otherwise, the dosing plan for cohort 2 will move forward into phase II expansion. The highest dose of pinometostat that is tolerated as described here will be considered the maximally tolerated dose (MTD).

[figure not shown]

Figure 1. A standard 3+3 dose escalation. With only two cohorts (dose levels), escalation stops

after cohort 2; if 2-3/3 DLT at dose level 1 (cohort 1), a safety review will be initiated to decide whether dose level reductions below the starting dose should be considered.

The phase 2 expansion phase will use the maximum tolerated dose/schedule as determined by phase 1b above and accrue additional patients to gather preliminary evidence of efficacy. Patients will be treated in the same manner as in the phase 1b portion above, with the exception that only a single dose level/cohort will be expanded.

The expansion cohort will comprise 4-25 patients who will be treated at the maximum tolerated dose schedule (see below; phase 1b patients who were treated at the MTD will be included in the statistical analysis of efficacy together with phase 2 patients, which in total comprises 10-31 patients).

Patients requiring re-induction, if any, will be treated at the assigned dose of pinometostat. Patients undergoing re-induction treatment will be analyzed jointly with patients not requiring re-induction for analysis of the primary efficacy endpoint, but a subgroup analysis consisting only of patients who did/did not require a second induction may be conducted.

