The primary efficacy objective is to calculate the rate of complete response (CR) or complete response with incomplete count recovery (CRi) after combination treatment and the primary efficacy hypothesis is that the rate of CR will be higher than among historical controls.

H0: The CR rate is $\leq 65\%$

Ha: The CR rate is $\geq 85\%$

We will use a Simon two-stage design (minimax) to test the hypothesis that the CR rate is greater than 65%. Assuming that the true CR rate among those treated is at least 85%, and setting type I and type II error rates to 10% (yielding $\alpha=\beta=0.1$), we will enroll 13 patients in the first stage. If 8 or fewer responses are observed during stage 1, the study will be stopped early. If there are 9 or more responses, an additional 18 patients will be enrolled in stage 2 for a total of 31 patients. At the completion of the second stage, the drug will be declared efficacious and the probability of an unacceptable CR rate $\leq 64\%$ ruled out if at least 24 CRs are observed out of all 31 patients. This design has a 90% power to correctly rule out a CR rate $\leq 65\%$ if the true rate is 85%, with a type 1 error rate of 0.0951.

| | |
|-----------|----|
| N | 31 |
| n1 | 13 |
| r1 | 8 |
| n2 | 18 |
| r2 | 23 |

NOTE: Patients treated at the maximum tolerated dose in the phase 1b portion (3, or 6) will be counted toward the total needed to satisfy the statistical design. This means that possible total accrual ranges for the whole trial are not $[6, 12+31] = [6, 43]$ but $[6, 12 + 31 - 6] = [6, 37]$

For both phases, early response evaluation will occur at day 21 (day 14 of 7+3) with a bone marrow examination, and if $> 5\%$ myeloid blasts are seen, or $\leq 5\%$ myeloid blasts but with an

aberrant immunophenotype matching the pretreatment immunophenotype, a re-induction attempt may be made with 5 and 2 days of cytarabine and daunorubicin, respectively, both medications at the same doses as initial induction. Pinometostat will be given at 90 mg/m², unless 60 mg/m² was previously established as the RP2D, in which case it shall be given at 60 mg/m². The clock will be reset, and pinometostat will be administered for an additional 28 days (unless stopped early for reasons of toxicity, withdrawal from study, or death).

Exploratory pharmacodynamics biomarkers will be collected at screening, at day 8, and at relapse if applicable for both phases (these are described above).

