f. Long-term follow-up for survival should be conducted at least monthly after patient has completed treatment and should include reporting of survival, subsequent therapy, transplant (if performed). This should be done in person if patient is being followed clinically at the treating center, or by telephone otherwise. After 1 year, this can be done every 3 months. After 5 years, further follow-up is not required.

Table 11.2: Treatment plan for re-induction.

| | Wk 1 | Wk 2 | Wk 3 | Wk 4 | Off Study ^c | Long Term Follow-Up ^g |
|---|----------------|----------------|---------|----------------|------------------------|-------------------------------------|
| Pinometostat | A | A | A | A | | |
| Cytarabine | B | | | | | |
| Daunorubicin | C | | | | | |
| Concurrent meds | X | X | X | X | | |
| Physical exam | X | X | X | X | X | |
| Vital signs | X | X | X | X | X | |
| Height and Weight | X | X | X | X | X | |
| Performance status | X | X | X | X | X | |
| CBC w/diff, plts, PT/INR, aPTT | X | X | X | X | X | |
| Serum chemistry ^a | X | X | X | X | X | |
| Echocardiogram/MUGA ^f | X ^f | | | | | |
| Adverse event evaluation | X | X | X | X | | |
| Bone marrow aspiration and biopsy | | X | | X ^d | | |
| Bone marrow metaphase karyotype | | X | | X ^d | | |
| Bone marrow MLL (KMT2A) translocation by FISH | | X | | X ^d | | |
| Immunophenotyping (BM and PB) | | X | | X ^d | | |
| Differentiation analysis | | X ^e | | X ^d | | |
| Comprehensive mutational profile | | X ^e | | X ^d | X | |
| Survival | | | | | | X ^g |

A: Pinometostat: Dose as assigned; weeks 1-4, days 1-28 of a “reset” calendar where day 1 is the start of 5+2 reinduction
 B: Cytarabine: 100 mg/m2 continuous IV infusion; days 1-5 of re-induction
 C: Daunorubicin: 60 mg/m2 IV; daily days 1,2 of re-induction
 a Albumin, alkaline phosphatase, total bilirubin, bicarbonate, BUN, calcium, chloride, creatinine, glucose, uric acid, LDH, phosphorus, potassium, total protein, SGOT [AST], SGPT [ALT], sodium.
 b. Serum pregnancy test (women of childbearing potential).
 c. Off-study evaluation.
 d. At count recovery in week 4 or beyond
 e. Day 8 of week 2, and at relapse (if applicable), and off-study
 f. Echocardiogram or MUGA should demonstrate EF ≥45% before the second induction cycle (“re-induction”) is initiated

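### The re-induction dose rule has no exception for a patient already reduced for toxicity, and no section says that Section 7's bar on escalation governs

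*Combined protocol and SAP*

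**What the plan says.** All references are to the combined protocol and SAP.

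- **Re-induction dose.** Section 6.1.3 applies its table to every re-induced patient in either phase. The pinometostat dose is 90 mg/m²/day for 28 days, unless 60 "has been previously identified as the maximum tolerated dose after completion of the Safety Run-in Phase". Section 9.1 repeats this with a different term: 90 unless 60 "was previously established as the RP2D, in which case it shall be given at" 60.
- **Assigned dose.** Elsewhere in 9.1: "Patients requiring re-induction, if any, will be treated at the assigned dose of pinometostat". Table 11.2, footnote A, reads "Dose as assigned; weeks 1-4, days 1-28 of a" reset calendar. Neither place says what this means for a patient whose dose has been changed.
- **Reductions.** For a possibly related Grade 3 event outside the listed exclusions, Section 7 has sites hold pinometostat until recovery, "then re-initiate with a one-third dose reduction". Recurrence or Grade 4 means stopping.
- **Escalation.** Section 7 also says: "No intra-patient escalation of study drug is permitted, except as outlined below and with permission of principal investigator". Re-induction is not among the exceptions. The Grade 3 row refers to the exceptions under dose-limiting toxicity. There, 6.2 lets certain transient events restart at 60 and go back up if the patient was on 90 ("otherwise not applicable) if it does not recur").
- **Cohort 1 schedule.** 90 mg/m² on days 1-7, "then decrease dose to 60 mg/m² CIVI for days 8-35". Cohort 2 receives 90 throughout, including with chemotherapy.

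**The concern.** Re-induction is decided on the day 21 marrow, so a patient may already have been cut for a related Grade 3 event. The re-induction table then gives a number that ignores the cut. A site that follows the table raises the dose of a drug that has just caused a suspected Grade 3 toxicity, and gives it with 5+2. A site that follows Section 7 keeps the lower dose. At stake are patient safety and consistent dosing.

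A second gap concerns patients with no toxicity. A Cohort 1 patient is on 60 from day 8. If that patient is re-induced before the run-in has fixed the MTD, 6.1.3 and the numeric rule in 9.1 give 90, while the other 9.1 sentence and Table 11.2 point to the assigned dose. Giving 90 together with chemotherapy is what Cohort 2 is there to test, after Cohort 1 has cleared.

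**Working it through.** **Inputs.** Re-induction dose 90, or 60 if that is the MTD or RP2D (6.1.3, 9.1); 28 days of pinometostat at re-induction (6.1.3); one-third reduction (Section 7); Cohort 1 and Cohort 2 schedules and 3-6 patients per cohort (9.1). I take 60 being the MTD to mean that the Cohort 1 schedule was selected.

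**Reproducing the plan's own figures.** Reduced dose = dose × (1 − 1/3). 90 × 2/3 = 60 and 60 × 2/3 = 40, as in Section 7's examples.

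**Difference between readings.** Relative increase = (dose under 6.1.3 and 9.1 ÷ dose kept under Section 7) − 1. The 28-day total is 28 × daily dose: 28 × 90 = 2,520; 28 × 60 = 1,680; 28 × 40 = 1,120 mg/m².

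| Path | Dose kept | Dose under 6.1.3/9.1 | Increase | 28-day totals (mg/m²) |
|---|---|---|---|---|
| A. 90 schedule (Cohort 2, or phase 2 at 90), cut 90 to 60 | 60 | 90 | 90/60 = 1.50, +50% | 1,680 vs 2,520 (+840) |
| B. Cohort 1 run-in, cut 90 to 60 in week 1 and kept at 60, re-induced before the MTD is set | 60 | 90 | +50% | 1,680 vs 2,520 (+840) |
| C. Phase 2 on the Cohort 1 schedule, cut 60 to 40 | 40 | 60 | 60/40 = 1.50, +50% | 1,120 vs 1,680 (+560) |
| D. Cohort 1 run-in, cut 60 to 40 from day 8 on, re-induced before the MTD is set | 40 | 90 | 90/40 = 2.25, +125% | 1,120 vs 2,520 (+1,400) |
| E. Phase 2 on the Cohort 1 schedule, cut 90 to 60 in week 1 and kept at 60 | 60 | 60 | 60/60 = 1.00, none | 1,680 both |
| F. Cohort 1 run-in, never reduced, re-induced before the MTD is set | 60 (days 8-35 dose) | 90 | +50% | 1,680 vs 2,520 (+840) |

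Path D can affect at most 6 patients, the most that Cohort 1 can hold. Paths B and E assume that a patient cut to 60 in week 1 stays at 60 from day 8; the plan does not say whether the scheduled step to 60 is itself cut by a third. Path F is not a toxicity reduction, so it is a separate gap.

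**Which rule prevails.** 6.1.3 does not mention Section 7, and Section 7 does not mention re-induction. Section 7 joins its two conditions for escalation with *and*: the increase must be outlined and the principal investigator must permit it. Permission alone does not meet that wording. Path F shows that 6.1.3 itself schedules an increase that Section 7 does not list, so the two sections were not fully reconciled.

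**Simon design.** With stage 1 stopping at 8 or fewer of 13, and success at 24 or more of 31, P(success) = Σ over x = 9 to 13 of C(13,x) pˣ(1−p)¹³⁻ˣ × P(Bin(18,p) ≥ 24 − x). At p = 0.65 this is 0.0951; at p = 0.85 it is 0.9036. Both match 9.1. Dose is not an input.

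**The case against.** The strongest reply is that no real conflict exists. The tables in 6.1.1 and 6.1.2 are equally silent on reductions, and nobody reads them as overriding Section 7. Section 6.1 opens by pointing to the dose modifications (it cites Section 6, apparently a slip for Section 7). On that reading 6.1.3 gives the scheduled dose and Section 7 modifies it. This largely stands. A reader might infer that the protocol directs sites to reverse toxicity reductions, or that the two readings carry equal weight. The documents do not support either inference, because Section 7 bars escalation expressly. What remains is that no text says Section 7 governs at re-induction.

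A second reply is that path F follows a planned schedule and returns to a dose the patient already had in days 1-7. That is right as far as it goes, and path F does not show that a toxicity cut may be reversed. But the earlier exposure was without chemotherapy.

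A third is that few patients are involved and that they are watched. Section 2.2.3 gives some toxicity counts: among 49 adults, Grade 3 or higher non-hematologic events of hypophosphatemia (1), decreased ejection fraction (3) and transaminases (1), and dose-limiting toxicity in 4 of 18 children. These are monotherapy figures in relapsed or refractory disease, and the adult list may be incomplete. No re-induction rate is given. Assume 20% to 50%, independence, and each adult event in a different patient. At the maximum accrual of 37:

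- 37 × 5/49 × 0.20 to 0.50 gives about 0.8 to 1.9 patients;
- 37 × 4/18 × 0.20 to 0.50 gives about 1.6 to 4.1 patients.

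Some of these would drop out, because exempt events, the 6.2 re-escalation route and discontinuation remove them. The combination could be more toxic than monotherapy, so these are illustrations and not bounds.

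The safeguards are real:

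- In the run-in, a related toxicity that the investigator judges to need a dose reduction is itself a DLT (6.2), which sites are expected to report (6.3).
- Escalation under Section 7 needs principal investigator permission.
- Ejection fraction must be at least 45% before re-induction (Table 11.2, footnote f).
- There are at least monthly phase 1 calls with CTEP (13.1) and two-weekly site calls (13.3).

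They make an unnoticed error less likely, but none of them states the dose.

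**Conclusion.** The point holds as a minor to moderate safety clarification. For a patient reduced before re-induction, the literal rule in 6.1.3 and 9.1 exceeds the dose Section 7 would keep by 50% on the usual paths. It exceeds it by 125% at most, on one narrow path open to no more than 6 Cohort 1 patients; path E shows no difference. The 125% figure should not be read as typical. Separately, the dose for an unreduced Cohort 1 patient re-induced during the run-in is stated inconsistently, 60 or 90.

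This rests on reading Section 7's bar as continuing into re-induction, which its wording favors but does not say. The number affected is small but cannot be fixed from the documents.

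A reader might also infer that the ambiguity weakens the efficacy test. It does not: the Simon type I error and power stay as stated. Patients permanently stopped are not part of the conflict, since Section 7, 6.5 and the early-stopping clause in 9.1 already point to giving no more drug.

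**What to change.** In 6.1.3 and the matching sentence of 9.1:

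1. State that a patient reduced under Section 7 is re-induced at the lower of the protocol re-induction dose and the patient's last reduced dose, unless re-escalated under the 6.2 exception with principal investigator permission.
2. For Cohort 1 patients re-induced before the MTD is set, state whether the dose is 60 (their days 8-35 dose, and the safer default) or 90. If it is 90, list it in Section 7 as an exception.
3. State that the assigned dose in 9.1 and in Table 11.2, footnote A, means the dose given by these rules.

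Two clerical additions can go with these: say outright that no pinometostat follows a Section 7 discontinuation, and correct the dose-modification pointers in 6.1 and 6.2 from Section 6 to Section 7.

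The cost is a few sentences, with no added patients, visits or procedures. Make the change before any run-in patient is re-induced. The amendment that 13.1 requires before phase 2 comes after the run-in, too late for the Cohort 1 patients in whom the largest gap arises.

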6.1.4 Pinometostat (CTEP IND Agent)

There are no known prophylactic or supportive care regimens required for pinometostat. There are no special precautions or relevant warnings associated with pinometostat. Pinometostat is given as IV continuous infusion administered at a constant flow rate for up to 90 hours. Pinometostat must be diluted in 0.9% sodium chloride to a final concentration between 0.54 mg/ml and 5.63 mg/ml prior to administration. Refer to section 8.1 for compatible IV infusion bags and sets.

6.1.5 Daunorubicin and Cytarabine

Supportive care for both cytarabine and daunorubicin involves administering oral ondansetron 16 mg every 24 hours for the full 7 days (5 days if in re-induction) of treatment, as well as oral dexamethasone 8 mg every 24 hours for the first 3 days (2 days if in re-induction) of treatment. For prophylactic treatment patients are given anti-fungal prophylaxis with oral posaconazole delayed release tablet beginning after the completion of daunorubicin and at a dose of 300 mg twice daily as a loading dose on the starting day, followed by 300 mg daily thereafter. Azole prophylaxis should be discontinued temporarily (i.e., not to overlap with anthracycline) in the event of re-induction.

Daunorubicin has Y-site intravenous incompatibility with cefepime hydrochloride, dexamethasone sodium phosphate, furosemide, heparin sodium, levofloxacin, pantoprazole, Piperacillin sodium-tazobactam sodium, and Sulfamethoxazole-trimethoprim among others. Daunorubicin has admixture intravenous incompatibility with dexamethasone sodium phosphate and heparin sodium. Cytarabine has Y-site intravenous incompatibility with allopurinol sodium, amiodarone, amphotericin B conventional colloidal, and daptomycin among others. Cytarabine has admixture intravenous incompatibility with heparin sodium, and regular insulin among others.

Daunorubicin should be prepared by injecting the calculated patient dose into 50-100 mL of 0.9% (normal) saline, and should be administered over 10-30 minutes in a free-flowing IV. The IV push route is not recommended.

Cytarabine should be prepared by diluting the calculated patient daily (24 hour) dose in a 1,000 mL bag of 0.9% (normal) saline, and administered by continuous IV infusion at a rate sufficient to achieve 100 mg/m² in 24 hours.

